## 8.2 Imaging during the Study

The parameters used to acquire each image in this study are outlined in the Subject Imaging Manual. The image review charter provides detailed descriptions of all imaging procedures, including baseline imaging, as well as the process used for spatial colocalisation of lesions on PET images.

## **8.2.1 Zr-TLX250 PET / CT Imaging**

### **8.2.1.1 PET/CT Imaging**

Abdominal PET/CT scans including the kidneys will be acquired over 20 minutes in a single bed position at a single time point on Day 5 ± 2 post administration (p.a.) of Zr-TLX250 using static image acquisition and low dose CT without contrast agent.

Patients found to have evidence of N1 or M1 disease may undergo additional whole body imaging (skull base to mid-thigh) using 6-8 bed positions with 10 minute acquisition time per bed position at the discretion of the treating clinician to support comprehensive staging. The additional scan if requested by the treating physician needs to be completed on Day 5 ± 2 post administration of the investigational product.

## **8.2.2 Imaging Analysis**

Reading for the co-primary endpoints (sensitivity and specificity) will be conducted independently by 3 trained readers, blind to history, and histology results.

Details of the assessments are described in the Image Review Charter that will be provided to the central reviewer.

### **8.2.2.1 Qualitative Zr-TLX250 Tumour Targeting**

Zr-TLX250 tumour uptake will qualitatively be assessed (yes /no), considering whether or not Zr-TLX250 binding inside or in the vicinity of the target lesion, as delineated on structural imaging (contrast-enhanced pre-BL imaging), can be detected.

Local and central reviewers will designate the lesions as having a status of positive (ccRCC) or negative (other than ccRCC). The interpretation of the Zr-TLX250 PET/CT images as positive or negative for ccRCC will be made on the basis of visual examination only.

The lesion will be classified as PET-positive if:

- Radioactivity in the lesion is clearly visible, AND
- Radioactivity in the lesion is greater than that in normal tissue (for example, in ipsilateral or contralateral kidney)

If these two criteria are not met, the lesion will be classified as negative. A Zr-TLX250 PET/CT scan is considered positive, if there is at least one positive tumour lesion.

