### **8.2.2.5 Independent Central Review of PET/CT Images**

A blinded central review of the Zr-TLX250 PET/CT images will be undertaken by an Independent Review Committee (IRC) consisting of 3 experienced reviewers not involved in the conduct of the trial. Reviewers will be independent of the study and without affiliation to the trial Sponsor. They will be blinded with regard to institution, histopathological diagnosis and clinical data. The central PET/CT reviewers will be asked to evaluate both kidneys and the link to the actually operated kidney will be done on the basis of the local pathology report retrospectively. This evaluation will be based on PET/CT images (low dose CT proportion without contrast) only.

Image sets covering extra-renal body regions will have all assessments conducted in the same way by blinded readers. The readers will localise the region within the body of the lesion of interest and then identify it as PET positive or PET negative, based on comparative regional uptake of activity. The readers will be blinded to the histology information on the tissue in question. In the event of multiple non-target lesions, the largest 2 lesions as determined by longest diameter, in each organ, will be evaluated for PET response.

Image data analyses will be performed by a central image core lab. Qualitative visual analysis (presence or absence of localised Zr-TLX250 uptake inside or in vicinity of the target lesion, as seen on contrast-enhanced pre-BL imaging), will be used to assess test performance of Zr-TLX250

PET/CT imaging to non-invasively detect ccRCC, using histological results from the central histological reference laboratory as standard of truth.

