### 8.3 Determination of Histological Standard of Truth

Partial and total nephrectomy are routinely used in the management of cT1 renal tumours.

All patients enrolled in the study will already be scheduled for partial nephrectomy or total nephrectomy as part of standard work-up and management of an indeterminate renal mass.

A small number of patients may be found to have an extra-renal focus of increased radioactivity accumulation that is suspicious for metastatic disease. In these patients, the investigator may elect to undertake further diagnostic work-up including additional imaging, which may result in a change in surgical strategy. Results of the PET scans should not dictate clinical management.

If results of further standard workup confirm metastatic disease, then biopsy might be performed. Biopsy results will be considered in the exploratory analysis (See Section 9.1.2.7).

The resected lesion will be localised by the site surgeon or pathologist using the localisation scheme in 8.1.4 above. The independent image readers will not have access to this evaluation.

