### 9.1 List of Variables and Population Characteristics

#### 9.1.1 Co-Primary Variables

The primary study objective is to evaluate the diagnostic efficacy in all patients by comparing the sensitivity and specificity of Zr-TLX250 PET/CT imaging to thresholds of 0.70 (sensitivity) and 0.68 (specificity), using histology as standard of truth.

The co-primary variables of this study will be the sensitivity and specificity of Zr-TLX250 PET/CT imaging to detect ccRCC.

- a) Sensitivity is defined as the proportion of study patients with a true positive (TP) Zr-TLX250 PET/CT scan (detection of clear cell carcinoma), relative to those with positive histopathological diagnosis for ccRCC:

$$\text{Sensitivity (\%)} = \text{TP} / (\text{TP} + \text{FN})$$

- b) Specificity is defined as the proportion of study patients with a true negative (TN) Zr-TLX250 PET/CT imaging result (no ccRCC), relative to those with a negative histopathological diagnosis of non-ccRCC (histological result:= TN + FP):

$$\text{Specificity (\%)} = \text{TN} / (\text{TN} + \text{FP})$$

The sensitivity and specificity of Zr-TLX250 PET/CT imaging will be compared separately to their respective prespecified thresholds. The comparison of sensitivity/specificity data will be based on data from the following 2x2 table (Table 5) which summarises the results of the qualitative Zr-TLX250 tumour targeting (tracer uptake in target lesion: yes/no) as determined by visual reading and the central study pathology as standard of truth.

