9 ANALYSIS VARIABLES

9.1 Co-primary Variables

The primary study objective is to evaluate the diagnostic efficacy in all patients by comparing the sensitivity and specificity of ⁸⁹Zr-TLX250 PET/CT imaging to thresholds of 0.70 (sensitivity) and 0.68

(specificity), using histology as standard of truth. The co-primary variables of this study will be the sensitivity and specificity of ⁸⁹Zr-TLX250 PET/CT imaging to detect ccRCC.

- a) Sensitivity is defined as the proportion of study patients with a true positive (TP) ⁸⁹Zr-TLX250 PET/CT scan (detection of clear cell carcinoma), relative to those with positive histopathological diagnosis for ccRCC:

$$\text{Sensitivity (\%)} = \left[\frac{\text{TP}}{\text{TP} + \text{FN}} \right] \times 100$$

- b) Specificity is defined as the proportion of study patients with a true negative (TN) ⁸⁹Zr-TLX250 PET/CT imaging result (no ccRCC), relative to those with a negative histopathological diagnosis of non-ccRCC (histological result:= TN + FP):

$$\text{Specificity (\%)} = \left[\frac{\text{TN}}{\text{TN} + \text{FP}} \right] \times 100$$

The sensitivity and specificity of ⁸⁹Zr-TLX250 PET/CT imaging will be compared separately to their respective prespecified thresholds. The comparison of sensitivity/specificity data will be based on data from the following 2x2 tables (Table 3), which summarises the results of the qualitative ⁸⁹Zr-TLX250 tumour targeting (tracer uptake in target lesion: yes/no) as determined by visual reading and the central study pathology as standard of truth.

Table 3: Probability Calculated on All Cases with Positive Histopathology

		Reference Standard Histopathology (standard of Truth)		Total
		positive (ccRCC)	negative (no ccRCC)	
Outcome ⁸⁹ Zr-TLX250 PET/CT scan	positive (ccRCC)	TP	FP	# of cases with positive PET/CT: TP+FP
	negative (no ccRCC)	FN	TN	# of cases with negative PET/CT:FN+TN
total		# of cases with ccRCC: TP+FN	# of cases without ccRCC: FP+TN	N

Abbreviations: FN = false negative; FP = false positive; TN = true negative; TP = true positive;

The point estimate of sensitivity of PET/CT is TP/(TP+FN) and the point estimate of specificity is TN/(TN+FP). Wilson's binomial (score) confidence intervals will be used to compare the 95% confidence interval lower boundary of each quantity to the threshold of 0.70 (sensitivity) and 0.68 (specificity).

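### The protocol gives two rules for a positive PET result, target lesion and any lesion, and neither document says which fills the co-primary 2x2 table or that a positive call must match the lesion that supplies the histology

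*Protocol*

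**What the plan says.** **Index test.** Protocol 8.2.2.1 opens with a lesion-level read: "binding inside or in the vicinity of the target lesion, as delineated on structural imaging". It closes with a scan-level rule: a "PET/CT scan is considered positive, if there is at least one positive tumour lesion". The SAP does not repeat the second rule.

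**Endpoint.** Protocol 9.1.1 and SAP 9.1 work at scan level: "Sensitivity is defined as the proportion of study patients with a true positive (TP") scan among those with ccRCC on histology, with the mirror definition for specificity. The rows of protocol Table 5 and SAP Table 3 are labelled by PET/CT scan outcome. The sentence that introduces these tables describes the input as "tracer uptake in target lesion: yes/no) as determined by visual reading and the central study pathology as standard of truth". The synopsis uses the same target-lesion wording.

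**Linking image to tissue.** Under protocol 8.2.2.5 the central readers "evaluate both kidneys and the link to the actually operated kidney will be done on the basis of the local pathology report retrospectively". Extra-renal regions, where imaged, are read in the same way: "In the event of multiple non-target lesions, the largest 2 lesions as determined by longest diameter, in each organ, will be evaluated". Under 8.1.4 the site and the readers record kidney and segment independently. Under 8.3, "The resected lesion will be localised by the site surgeon or pathologist using the localisation scheme in 8.1.4 above". Section 8.2 leaves the co-localisation process to the image review charter.

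**Standard of truth.** Section 8.3.2 names the central diagnosis of the renal mass. Protocol Table 2 keeps patients with N1 or M1 disease on PET in the full analysis set and accepts histology from any lesion, primary or metastatic. Protocol 9.2.1 and SAP 10.1 also accept extra-renal biopsies. Section 8.3 assigns biopsy results to the exploratory analysis.

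**The concern.** The claim to be supported is that PET classifies the indeterminate mass as ccRCC or not. The 2x2 entry must therefore pair a read of one lesion with the histology of that same lesion. As written, a programmer could fill the table either way, and the only sentence that defines a positive scan is the any-lesion one.

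Two patients show the difference:

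- The mass is ccRCC and reads negative, but another focus reads positive. The any-lesion rule gives TP and the target-lesion rule gives FN.
- The mass is not ccRCC and reads negative, but another focus reads positive. The any-lesion rule gives FP and the target-lesion rule gives TN.

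Both co-primary endpoints are affected, in opposite directions. The shift in sensitivity favours the product. Specificity has the smaller denominator, so a few patients matter there. If the choice is left until reads and histology are merged, a confirmatory endpoint is being defined after the data are known.

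**Working it through.** **1. Which foci could matter.**

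- Another site in the operated kidney: not screened out, because the link is to the kidney and not to the lesion.
- An extra-renal focus: read in the same way where imaged, and no text keeps it out of the scan result.
- The other kidney: largely covered by the retrospective link to the operated kidney.

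**2. Direction.** Let q be the chance that a reader marks a positive focus other than the lesion that supplies the histology, taken as independent of the read of that lesion. Then:

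- any-lesion specificity = Sp × (1 − q)
- any-lesion sensitivity = Se + (1 − Se) × q

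The any-lesion rule can turn a negative into a positive but never the reverse. The direction therefore holds for any q and does not need independence.

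**3. Inputs from the plan** (protocol 9.3.1, SAP 7): true sensitivity and specificity 0.83; thresholds 0.70 and 0.68; two-sided 95% Wilson interval; 70% cT1a with 34% non-ccRCC; 30% cT1b with 17% non-ccRCC.

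- Non-ccRCC share: 0.70 × 0.34 + 0.30 × 0.17 = 0.289.
- N=252 (protocol): 252 × 0.289 ≈ 73 non-ccRCC and 179 ccRCC.
- N=300 (SAP 5.1 and 6): 300 × 0.289 ≈ 87 non-ccRCC.

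**4. Pass marks for specificity** (Wilson lower limit above 0.68).

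- n=73: 58 needed (lower limit 0.688; 57 gives 0.673).
- n=87: 68 needed (lower limit 0.684; 67 gives 0.671).

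**5. The plan's own figure.** The plan states 90% power at N=252. The exact binomial chance of at least 58 of 73 at 0.83 is 0.833, so 90% is not reproduced. That is a separate sample-size matter; 0.833 serves here only as the starting value.

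**6. Illustration.** The documents do not give q; 1%, 3% and 5% are assumptions.

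| q | Any-lesion specificity | One reader passes, n=73 | One reader passes, n=87 | Any-lesion sensitivity |
|---|---|---|---|---|
| 0 | 0.830 | 0.83 | 0.91 | 0.830 |
| 1% | 0.822 | 0.78 | 0.87 | 0.832 |
| 3% | 0.805 | 0.66 | 0.76 | 0.835 |
| 5% | 0.789 | 0.52 | 0.62 | 0.839 |

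At n=73 the expected number of extra false positives is 73 × 0.83 × q: 0.6, 1.8 and 3.0 patients. At smaller assumed rates of 0.2% and 0.5% the chance of passing is 0.82 and 0.81.

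**7. Error rate for sensitivity.** With 179 ccRCC patients the pass mark is 138. If the true lesion-level sensitivity is exactly 0.70, the any-lesion value is 0.70 + 0.30q. The chance that one reader passes rises from 2.1% to 2.6%, 3.8% and 5.5% at the same three rates.

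All these are chances for one reader on one endpoint. The success rule needs the same two of three readers on both endpoints.

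**The case against.** The strongest reply is that this is one stray sentence. Target-lesion wording recurs throughout both documents, including the text that introduces the 2x2 table, and the SAP omits the any-lesion rule. A sensible analyst would use the target lesion. There are also real safeguards: a single mass at entry, a routine scan of the abdomen only, readers' and surgeons' localisation by kidney and segment, documentation of where the specimen came from, the operated-kidney link, and extra-renal uptake listed as an exploratory variable. The charter may already hold the matching rule; it was not available for this review.

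Much of this stands. It makes affected patients uncommon and shows that the target lesion is probably what was meant. It does not remove the conflict. The definitions of sensitivity and specificity and the table rows refer to the scan, and the protocol's only definition of a positive scan is the any-lesion one. The entry criterion limits what earlier imaging showed, not what blinded readers mark on PET. The recorded segments are not used in any scoring rule in either document. A charter rule at lesion level would still contradict 8.2.2.1.

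Four stronger readings are tempting but not supported:

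- That the truth is the resected mass alone. Protocol Table 2, protocol 9.2.1 and SAP 10.1 also accept extra-renal histology.
- That the endpoint measures uptake anywhere in the body. The documents conflict on this; they do not settle on that endpoint.
- That uptake in the other kidney is a main route to error. The operated-kidney link largely deals with it.
- That the chance of passing specificity does fall to 0.52. That figure depends on an assumed 5% rate and on N=252.

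**Conclusion.** The plan holds two conflicting rules for the index test of its co-primary endpoints, and no stated requirement that the read and the histology refer to the same lesion. This is a conflict in the definition of a confirmatory endpoint, not merely missing detail, and it should be settled before analysis.

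The direction is certain: relative to the target-lesion rule, the any-lesion rule can only raise sensitivity and lower specificity. The size is unknown. The table in the working assumes a rate that the documents do not give, independence from the target read, and the planned 0.83 and 28.9% non-ccRCC. At rates well below 1% the effect is small; at a few per cent it would matter for specificity at either sample size. The varying source of truth makes the missing link more important, because no text says which read pairs with an extra-renal sample.

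**What to change.** 1. In protocol 8.2.2.1, delete the any-lesion sentence or limit it to a supportive scan-level summary.
2. In 8.2.2.1 and SAP 9.1, state that each reader's co-primary 2x2 entry is the call for the target lesion that supplies the histological standard of truth, linked by the recorded kidney and segment. Align the image review charter.
3. Where the reader's segment and the surgical segment differ, use a pre-specified adjudication blinded to histology. Do not score a mismatch automatically as negative. Central readers work from PET with non-contrast low-dose CT and do not see the site's localisation, so in patients with a single mass a mismatch may be a localisation error. Automatic scoring would then turn true positives into FN and false positives into TN, lowering sensitivity and raising specificity.
4. List other positive foci separately.
5. Reconcile protocol Table 2, protocol 9.2.1 and SAP 10.1 with protocol 8.3 on whether extra-renal histology enters the co-primary analysis.

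The cost is wording in three documents and adjudication of a few mismatches. No new data are collected and the sample size does not change.

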### **8.2.2.2 Quantitative Zr-girentuximab Tumour Targeting**

Absolute activity concentrations of tracer in tumour (MBq/cm^3) will be calculated using attenuation-corrected count rates, and tumour volumes, as determined by contrast-enhanced pre-BL MRI or equivalent imaging modality with contrast agent as part of the standard of care. Considering specific activity (MBq/mg), protein mass dose concentrations of tracer in tumour at the time point of imaging (mg/cm^3) will be calculated.

### **8.2.2.3 Estimation of Lu-girentuximab Tumour Targeting**

Protein mass dose concentrations of tracer in tumour (mg/cm^3) at the single time point of imaging, and a general model of average girentuximab kinetics in tumour over time (derived from sequential Zr-TLX250 biodistribution data), will be used, to estimate possible girentuximab protein kinetics in tumour lesions over a period of one week, assuming the kinetics of diagnostic Zr-girentuximab and therapeutic Lu-girentuximab are essentially similar. Such protein kinetic data can be used, to generate simulated time-activity curves for Lu-girentuximab in tumour for different specific activity levels, to yield estimates of achievable therapeutic absorbed doses to tumour (Gy).

### **8.2.2.4 Local Review of PET/CT Images**

Local image review will involve qualitative assessment only and will follow the same guidelines as being used for the qualitative independent, blinded review. However, local reviewers will not be blinded with respect to patient data.

### **8.2.2.5 Independent Central Review of PET/CT Images**

A blinded central review of the Zr-TLX250 PET/CT images will be undertaken by an Independent Review Committee (IRC) consisting of 3 experienced reviewers not involved in the conduct of the trial. Reviewers will be independent of the study and without affiliation to the trial Sponsor. They will be blinded with regard to institution, histopathological diagnosis and clinical data. The central PET/CT reviewers will be asked to evaluate both kidneys and the link to the actually operated kidney will be done on the basis of the local pathology report retrospectively. This evaluation will be based on PET/CT images (low dose CT proportion without contrast) only.

Image sets covering extra-renal body regions will have all assessments conducted in the same way by blinded readers. The readers will localise the region within the body of the lesion of interest and then identify it as PET positive or PET negative, based on comparative regional uptake of activity. The readers will be blinded to the histology information on the tissue in question. In the event of multiple non-target lesions, the largest 2 lesions as determined by longest diameter, in each organ, will be evaluated for PET response.

Image data analyses will be performed by a central image core lab. Qualitative visual analysis (presence or absence of localised Zr-TLX250 uptake inside or in vicinity of the target lesion, as seen on contrast-enhanced pre-BL imaging), will be used to assess test performance of Zr-TLX250

PET/CT imaging to non-invasively detect ccRCC, using histological results from the central histological reference laboratory as standard of truth.

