#### **8.1.4 Pre-baseline Morphological Imaging**

Patients with suspected ccRCC, typically receive abdominal MRI or CT with and without contrast agent as part of their initial diagnostic work-up. Contrast enhanced MRI or CT is also the standard for re-staging in patients after initial therapy. The imaging methodology will be conducted according to the institutional routine practise.

Pre-baseline images will be collected for evidence of a single indeterminate renal mass (IRM) and for precise volumetric tumour delineation.

[figure not shown]
A current contrast-enhanced abdominal MRI or equivalent standard of care imaging (based on national standards) with contrast agent, not older than 90 days on Day 0, but conducted before any screening procedure, should be available, providing evidence of a newly diagnosed, single renal mass, confined to the kidney, and measuring  $\leq 7$  cm in greatest diameter (stage cT1) (inclusion criterion). Ultrasound images will not be acceptable.

In the scope of this clinical study, no contrast-enhanced CT or MRI will be performed.

Lesions of interest will be spatially localised by the site and independently by the central image readers. The central image readers will not have access to the spatial localisation determined by the site. For lesions located within the kidney, spatial localisation should be conducted as follows

- Definition of the diseased kidney (left or right)
- Definition of the segment within the kidney containing the lesion. The segments are based on Figure 2
- In the event of a total nephrectomy the pathologist should specify the segment location that was used to provide the tissue samples used for central analysis

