#### 8.3.1 Local Pathology Assessment

Surgical resection material, along with appropriate documentation of its in situ origin, allowing identification with lesion localisation on PET images will be sent to the local pathology department for routine histological work-up (H&E staining, histological diagnosis: ccRCC vs. non-ccRCC).

If surgical material is taken from extra-renal locations then samples of this tissue should be prepared in the same way as renal samples and submitted for analysis in the same way.

The results from the local pathology assessment on diagnosis will not be part of the study.

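### Central reads are linked to the operated kidney from a pathology report whose work-up yields the ccRCC diagnosis, with no stated masking of the linker: an avoidable, probably small, exposure to bias.

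*Protocol*

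**What the plan says.** - **Linkage.** Under Protocol 8.2.2.5 the central readers evaluate both kidneys, and "the link to the actually operated kidney will be done on the basis of the local pathology report retrospectively".
- **Content of the local work-up.** Protocol 8.3.1 describes "routine histological work-up (H&E staining, histological diagnosis: ccRCC vs. non-ccRCC". It adds: "The results from the local pathology assessment on diagnosis will not be part of the study". The standard of truth is central histology (8.3.2).
- **Blinding.** Of the readers, 8.2.2.5 says: "They will be blinded with regard to institution, histopathological diagnosis and clinical data". Protocol 8.1.4 says: "The central image readers will not have access to the spatial localisation determined by the site". Nothing comparable is said about whoever makes the link.
- **Location data already recorded.** Readers and site each record kidney side and segment independently (8.1.4). After surgery, "The resected lesion will be localised by the site surgeon or pathologist using the localisation scheme in 8.1.4 above" (8.3). Protocol 8.3.1 also has the specimen travel with documentation of its origin, so that it can be identified with the lesion on PET.
- **Scoring.** Protocol 8.2.2.1 calls a scan positive if it shows at least one positive tumour lesion. Protocol 9.1.1 and SAP 9.1 build the co-primary 2x2 table from uptake in the target lesion.
- **Charter.** Protocol 8.2 says that the image review charter covers imaging procedures, "as well as the process used for spatial colocalisation of lesions on PET images". The charter is not among the documents reviewed.

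**The concern.** A blinded read becomes a true or false result only once it is tied to the operated side and, where segments are compared, to the resected lesion. That step comes after the reads and draws on a report that can be expected to carry the local diagnosis. The local diagnosis is not the study's truth, but local and central pathology examine the same tumour, so knowing one largely reveals the other.

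The step matters only where there is something to decide: a focus in a different segment from the resected mass, or in the other kidney. In those cases the two scoring rules give different answers:

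- In a non-ccRCC patient, an off-target focus is a false positive under the any-positive-lesion rule and a true negative under the target-lesion rule.
- In a ccRCC patient whose only focus is off target, the scan is a true positive under the first rule and a false negative under the second.

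A linker who knows the diagnosis and has no written rule could resolve each case in the favourable direction without intending to. Sensitivity and specificity would then rise together. One link can serve all three readers, so requiring success in the same two of three readers need not protect against it.

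**Working it through.** The plan gives no figure for linkage error, so there is none to reproduce. The calculation below only sizes what a few decisions could do.

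**Inputs (Protocol 9.1.1, 9.3.1; SAP 5.1)**
- Size mix 70% cT1a and 30% cT1b; non-ccRCC rates 34% and 17%. Non-ccRCC share = 0.7 × 0.34 + 0.3 × 0.17 = 0.289.
- N = 252 gives 0.289 × 252 ≈ 73 non-ccRCC and 0.711 × 252 ≈ 179 ccRCC patients. The SAP's N = 300 gives about 87 and 213.
- Success per reader: lower limit of the two-sided 95% Wilson interval above 0.68 (specificity) or 0.70 (sensitivity).

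**Step 1: pass marks.** With n = 73, the Wilson lower limit is 0.688 at 58 true negatives and 0.673 at 57, so 58 are needed. The same search gives 68 of 87, 138 of 179 and 163 of 213.

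**Step 2: relabelling k false positives as true negatives.** At true specificity 0.68, the per-reader chance of passing is P(X ≥ pass mark − k) with X ~ Binomial(n, 0.68). Here k is an assumption.

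| k | n = 73 (N = 252) | n = 87 (N = 300) |
|---|---|---|
| 0 | 2.1% | 2.5% |
| 1 | 3.9% | 4.3% |
| 2 | 6.8% | 7.0% |
| 3 | 11.0% | 10.8% |

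For scale, 73 × 0.32 = 23.4 false positives are expected, so k = 1 to 3 means 4% to 13% of them.

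**Step 3: a share d of doubtful matches, all resolved towards the truth.** The apparent rate becomes p + d(1 − p). The documents give no value for d, so a range is shown (N = 252, per reader, true value at the threshold).

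| d | Specificity passes | Sensitivity passes |
|---|---|---|
| 0 | 2.1% | 2.1% |
| 1% | 2.4% | 2.6% |
| 2% | 2.8% | 3.2% |
| 5% | 4.1% | 5.5% |
| 10% | 7.3% | 12.4% |

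At d = 5% the shift in the rate itself is 0.05 × 0.32 = 1.6 points for specificity and 0.05 × 0.30 = 1.5 points for sensitivity. At N = 300 and d = 5%, the chance of passing moves from 2.5% to 4.9% (specificity) and from 2.1% to 5.9% (sensitivity).

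**Step 4: the opposite extreme.** If every doubtful match is scored as an error, a true 0.83 becomes 0.83(1 − d). At N = 252 and d = 5%, per-reader power falls from 83% to 52% for specificity and from 98% to 75% for sensitivity. Such an analysis is useful as a bound but is too severe to be the success criterion.

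**What affects d.** A single eligible mass (4.2.1) keeps it low. Protocol 8.2.2.5 pulls the other way. It says that the central evaluation rests on PET and non-contrast CT alone, yet defines uptake relative to the lesion on contrast-enhanced pre-baseline imaging. If readers lack that imaging, segment disagreements become more likely.

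**The case against.** The case against is substantial, and most of it stands.

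- **The link is to the kidney, not the mass.** Left or right leaves little to judge, and eligibility requires one mass confined to one kidney. This narrows the point to uncommon cases. It does not remove it, because 8.1.4, 8.3 and 8.3.1 also foresee matching at segment or lesion level.
- **Vicinity is the reader's call.** Whether uptake near the lesion counts is part of the blinded read (8.2.2.1). The linker does not decide it; the linker can affect only which recorded focus counts.
- **The local diagnosis is kept out of the study data.** That is so, and truth is central. But the text does not say that the diagnosis is removed from the report used for linkage.
- **The charter may already contain a masked rule.** It may. The documents are silent on masking, and silence does not show that the step is unmasked.
- **The site's segment record is not certain to be free of the diagnosis.** A pathologist may complete it, so redaction reduces the exposure and may not remove it entirely.

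A reader might infer that both co-primary endpoints will be inflated. The documents do not support that: they give no rate of doubtful matches, no evidence of discretionary matching and no direction of error.

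**Conclusion.** The point holds as an avoidable exposure to bias. The protocol names a report from a diagnosis-yielding work-up as the source for a step that follows the reads. Neither document states masking of that step, and the protocol's two scoring rules disagree on off-target foci.

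The size is unknown and probably small. If 1% to 2% of matches were doubtful and all went towards the truth, the per-reader chance of a false pass would rise by about 0.3 to 1.1 points. At 5% it would roughly double for specificity and somewhat more than double for sensitivity. The relabelling figures (2.1% to 3.9%, 6.8% and 11.0%) rest on assumed counts. All of these are per-reader, single-endpoint figures and not the trial's error rate. Success needs both endpoints in the same two of three readers, and its error rate would depend on a between-reader correlation that the documents do not give.

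**What to change.** In Protocol 8.2.2.5 and SAP 9.1:

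1. Make the link from an extract of the side and segment already recorded under 8.1.4 and 8.3, with the diagnosis redacted. Where possible, have that location recorded before the diagnosis is known.
2. Assign the link to existing staff without access to local or central histology.
3. Pre-specify what counts as a match and how an unmatched focus is scored, including one in the other kidney. Reconcile the any-positive-lesion rule in 8.2.2.1 with the target-lesion table in 9.1.1.
4. Lock the link table before histology is merged.
5. Report the number of doubtful matches, with a sensitivity analysis that counts them as errors.
6. Clarify in 8.2.2.5 whether central readers see the contrast-enhanced pre-baseline images.

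If the image review charter already has a masked match rule, cite it and align 8.2.2.5 with it. The cost is minor data-management work and a few sentences in each document. No extra reads, visits or staff are needed.
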